6.1.1.1.2. Supplemental Analysis

To support the assessment of local reactions, the following endpoints (as defined in Section 3.1.1.1) will be summarized with the same analysis time point and analysis population as above and the appropriate analysis methodology and reporting results:

- Duration (days) of each local reaction after vaccination in each arm (left and right deltoid).
- Onset day of each local reaction after vaccination in each arm (left and right deltoid).

These continuous endpoints will be summarized by displaying n, mean, median, standard deviation, minimum, and maximum for each vaccine group.

Figures:

Bar charts with the proportions of participants for each local reaction throughout 7 days after vaccination in each arm (left and right deltoid) will be plotted for each vaccine group. The bars will be divided into severity categories to highlight the proportions of participants by maximum severity.

6.1.1.2. Systemic Events

6.1.1.2.1. Main Analysis

- Estimand: The percentage of participants reporting systemic events (fever, fatigue, headache, chills, vomiting, diarrhea, new or worsened muscle pain, and new or worsened joint pain) for up to 7 days following vaccination (Section 2.2).
- Analysis set: Safety population (Section 4).
- Analysis time point: Up to 7 days following vaccination.
- Analysis methodology: Descriptive statistics (Section 5.2.1).
- Intercurrent events and missing data: Missing data will be handled as described in Section 5.3
- Reporting results: Descriptive statistics for each systemic event after vaccination will be presented by maximum severity and cumulatively across severity levels for each vaccine group. Descriptive summary statistics will include counts and percentages of participants with the indicated endpoint and the associated 2-sided Clopper-Pearson 95% CIs.

6.1.1.2.2. Supplemental Analysis

The following endpoints for assessment of systemic events will be summarized similarly to the assessment of local reactions:

- Duration of each systemic event after vaccination.
- Onset day of each systemic event after vaccination.

These continuous endpoints will be summarized by displaying n, mean, median, standard deviation, minimum, and maximum for each vaccine group.

The use of antipyretic medication (see Section 3.1.1.3) will be summarized similarly to systemic events, except that there is no severity level associated with the use of antipyretic medication.

Figures:

Bar charts with the proportions of participants reporting each systemic event throughout 7 days will be plotted for each vaccine group. The bars will be divided into severity categories to highlight the proportions of participants by maximum severity.

6.1.1.3. Adverse Events

6.1.1.3.1. Main Analysis

- Estimand: The percentage of participants reporting AEs from vaccination through 4 weeks after vaccination (Section 2.2).
- Analysis set: Safety population (Section 4).
- Analysis time point: From vaccination through 4 weeks after vaccination.
- Analysis methodology: Descriptive statistics (Section 5.2.1).
- Intercurrent events and missing data: Missing data will not be imputed, except for partial AE start dates (Section 5.3).
- Reporting results: Counts, percentages, and the associated 2-sided Clopper-Pearson 95% CIs of AEs within 4 weeks after vaccination will be provided for each vaccine group.

6.1.1.3.2. Supplemental Analysis

Related (per investigator assessment) AEs, severe AEs, immediate AEs (within the first 30 minutes after the study vaccination), and protocol-specified AESIs (defined in Section 8.4.8 of the protocol) will also be summarized by vaccine group.

Symptoms and measurements collected at cardiac evaluation visits for monitoring of potential myocarditis or pericarditis will be presented in a listing, regardless of confirmed diagnosis or not.

In addition to the protocol-specified AESIs, Pfizer also evaluates a dynamic list of AESIs that have specific MedDRA term search strategies during clinical and postauthorization safety data review and signal detection; these include AEs of interest for vaccines in general or due to an association with COVID-19, taking into consideration health authority lists of AESIs for COVID-19 vaccines. These AESIs will also be summarized by vaccine group.

All AEs after informed consent and prior to the first vaccination will not be included in the analyses but will be in the listing.

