## Age and Sex:

- 1. Male or female participants aged 50 years or older at Visit 1 (Day 1).
  - Refer to Appendix 4 for reproductive criteria for male (Section 10.4.1) and female (Section 10.4.2) participants.

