### 8.4.8. Adverse Events of Special Interest

The following events are protocol-specified AESIs:

- Confirmed COVID-19 diagnosis (clinical signs/symptoms and positive SARS-CoV-2 NAAT or antigen test) after Visit 1 through the end of the study.
- Confirmed diagnosis of myocarditis or pericarditis occurring after vaccination. See Section 8.10.5.
- Potential menstrual cycle disturbances. See Section 8.10.6.
- GBS.
- Neuritis, including Bell's palsy.
- Vasculitis.

AESIs are examined as part of routine safety data review procedures throughout the clinical trial and as part of signal detection processes. Should an aggregate analysis indicate that these prespecified events occur more frequently than expected, eg, based on epidemiological data, literature, or other data, then this will be submitted and reported in accordance with Pfizer's safety reporting requirements. Aggregate analyses of safety data will be performed on a regular basis per internal SOPs.

All AESIs must be reported as an AE or SAE following the procedures described in Section 8.4.1 through Section 8.4.4. An AESI is to be recorded as an AE or SAE on the CRF. In addition, an AESI that is also an SAE must be reported using Vaccine SAE Report Form or via PSSA.

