# 8.10.6. Additional Procedures for Monitoring of Potential Menstrual Cycle Disturbances

Any female study participant who reports any symptoms that may indicate a disturbance of their normal menstrual cycle (including, but not exclusively, heavy menstrual bleeding, amenorrhea, irregular periods) following receipt of study intervention until 6 months after the last vaccination should be specifically evaluated by the investigator. Details of the symptoms, menstrual history, and results of any investigations performed will be recorded in the CRF.

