# 2. Postmenopausal female:

- A postmenopausal state is defined as no menses for 12 months without an alternative medical cause. In addition:
  - A high FSH level in the postmenopausal range must be used to confirm a postmenopausal state in women under 60 years of age and not using hormonal contraception or HRT.
  - A female on HRT and whose menopausal status is in doubt will be required to use one of the highly effective nonestrogen hormonal contraception methods if she wishes to continue her HRT during the study. Otherwise, she must discontinue HRT to allow confirmation of postmenopausal status before study enrollment.

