4. ANALYSIS SETS (POPULATIONS FOR ANALYSIS)

Analysis populations are defined for the statistical analysis of safety and immunogenicity results in the table below. Data for all participants will be assessed to determine if participants meet the criteria for inclusion in each analysis population prior to releasing the database, and classifications will be documented per standard operating procedures.

| Participant Analysis Set | Description | |
|------------------------------|---|--|
| Screened | All participants who have a signed ICD. | |
| Randomized | All participants who are assigned a randomization number in the IRT system. | |
| Safety | All participants who receive at least 1 dose of the study intervention. | |
| Evaluable immunogenicity | All eligible assigned participants who receive the study intervention to which they are assigned, have at least 1 valid and determinate immunogenicity result from the blood sample collected within 27 to 42 days after vaccination, and have no other important protocol deviations as determined by the clinician. | |
| All-available immunogenicity | All assigned participants who receive the study intervention and have 1 valid and determinate immunogenicity result after vaccination. | |

Important protocol deviations will be determined by the clinician. An important protocol deviation is a protocol deviation that, in the opinion of the sponsor's clinician, would materially affect assessment of immunogenicity, eg, participant receipt of a prohibited vaccine or medication that might affect immune response or a medication error with suspected decrease in potency of the vaccine. The sponsor's medical monitor will identify those participants with important protocol deviations that result in exclusion from analysis populations.

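### Potential menstrual cycle disturbance can occur only in women, but the SAP's general rule would summarize it on the whole safety population, men included, which dilutes any rate reported

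*SAP*

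**What the plan says.** Protocol 8.4.8 includes this item in its list of AESIs: "Potential menstrual cycle disturbances. See Section 8.10.6". Section 8.10.6 defines who is evaluated, "Any female study participant who reports any symptoms that may indicate a disturbance of their normal menstrual cycle", and for how long, "following receipt of study intervention until 6 months after the last vaccination". It sets no menopausal criterion. Protocol 5.1 admits men and women from age 50 with no upper age limit.

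On the analysis side, SAP 6.1.1.3.2 states that "protocol-specified AESIs (defined in Section 8.4.8 of the protocol) will also be summarized by vaccine group" and names no analysis set for that summary. Two other places supply one. SAP 5.2 bases the safety analyses on the safety population, and SAP 6.1.1.3.1, the main AE analysis that this summary supplements, uses the same set. SAP Section 4 defines it as "All participants who receive at least 1 dose of the study intervention". The only subset analysis planned, in SAP 6.5, is by age group. Neither document gives a denominator by sex or menstrual status for this event.

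**The concern.** A percentage is informative only if the people in its denominator could have had the event. Here the event is specific to women, and the default denominator includes men. Both the observed percentage and its upper confidence limit would therefore be lower than the data on women support.

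The sponsor made this an AESI and wrote a dedicated monitoring section for it. Protocol 8.4.8 also says that AESI frequencies are judged against what would be expected, for example from epidemiological data. That is a comparison of absolute rates, which is where a diluted denominator does harm. At stake is the correct reading of one supplemental safety row, most of all when the count is 0 or very small.

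**Working it through.** **Inputs from the documents**
- About 640 participants randomized 1:1:1:1 (SAP 2.3), so 640/4 = 160 per group.
- Two-sided 95% Clopper-Pearson limits for binary endpoints (SAP 5.2.1).
- Detection probabilities in Protocol 9.5, Table 7.

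**Input that must be assumed**
- The share of women, w. The documents do not give it. I use 50%, with 40% and 60% as a range.

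**Step 1: reproduce the plan's own figure.** P(at least 1 event) = 1 − (1 − p)^N. With p = 1% and N = 160 this is 0.7997, against 0.80 in Table 7. With N = 80 it is 0.5525, against 0.55. So for an event confined to women, with 80 women per group, the relevant entry at a 1% true rate is 0.55 rather than 0.80.

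**Step 2: dilution of the rate.** With x cases, the plan's rate is x/160 and the rate among women is x/(160w). Their ratio is 1/w:
- w = 50%: 1/0.5 = 2.0
- w = 40%: 1/0.4 = 2.5
- w = 60%: 1/0.6 = 1.7

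**Step 3: upper limit with no cases.** Limit = 1 − 0.025^(1/N):

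| Denominator | N | Upper 95% limit |
|---|---|---|
| Whole group | 160 | 2.3% |
| Women, w = 60% | 96 | 3.8% |
| Women, w = 50% | 80 | 4.5% |
| Women, w = 40% | 64 | 5.6% |

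**Step 4: can the dilution be sized for women still menstruating?** Suppose half are women and 5%, 10% or 30% of them still menstruate. That gives 4, 8 or 24 at risk per group. Dilution would be 160/4 = 40, 160/8 = 20 or 160/24 = 6.7, and the zero-count limits 60.2%, 36.9% or 14.2%. Neither share is in the documents, and the answer changes 6-fold across plausible inputs. This step shows only that the 2-fold figure is a lower bound at w = 50%.

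**Step 5: comparison between groups.** Allocation is randomized in equal proportions, so the expected share of women is the same in each group and 1/w cancels from a ratio of rates. It does not cancel from an absolute rate, a difference in rates or an upper limit.

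**The case against.** The strongest reply is that the predicted output is partly inferred. SAP 6.1.1.3.2 promises a summary of AESIs, not a percentage or a confidence interval. SAP 3.1.1.4 allows summaries and/or listings. SAP 5.2.1 gives intervals only where applicable and requires n and N to be shown. The percentage estimand in SAP 6.1.1.3.1 covers 4 weeks, whereas this event is followed to 6 months. All of this stands, so the point is conditional: if a rate or limit is reported under the general rule, it is diluted. Showing N = 160 does not remove the problem, because it does not tell the reader how many were women.

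Three stronger readings are tempting and are not supported:
- *Only women still menstruating can have the event, so the rate is too low by 7 to 20 times.* Section 8.10.6 covers any female participant with suggestive symptoms. Bleeding in a woman classed as postmenopausal could be recorded. The factor rests wholly on assumed shares.
- *The childbearing-potential categories in Protocol 10.4.3 give the at-risk set.* They classify fertility, not menstruation. A premenopausal woman with bilateral salpingectomy is outside the childbearing category but may still menstruate. The documents also do not show that this status is in the database for all women; Section 8.10.6 describes recording menstrual history for those who report symptoms.
- *A zero count will be taken as evidence that the combination is safe in this respect.* Nothing in the plan says so. All analyses are descriptive, and no objective or stopping rule uses this rate.

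It can also be said that one denominator for all AE rows is an ordinary convention. That is so, but it suits events that every participant can have, and this AESI is by definition not one.

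**Conclusion.** The concern holds in a limited form. Following the plan counts men in the denominator of an event they cannot have, and the direction of the error does not depend on any assumption. Its size does: it is 2-fold at 50% women (upper limit with no cases 2.3% against 4.5%) and 1.7- to 2.5-fold over 60% to 40% women. If being at risk also requires current menstruation the dilution is larger, but the documents do not permit a figure. A reader might infer a bias between vaccine groups; equal randomization argues against a systematic one, although numbers of women may differ by chance because sex is not a stratification factor. No primary estimand and no part of the sample-size rationale changes. This is a cheap improvement to one supplemental summary.

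**What to change.** Add to SAP 6.1.1.3.2: *For potential menstrual cycle disturbances, the denominator is the number of female participants in the safety population in each vaccine group, and n/N is shown.* The safety-population figure may stay beside it.

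If menstrual status at Visit 1 is already in the database, also show, per group, the number of women who are not postmenopausal, hysterectomized or bilaterally oophorectomized. Do not remove women for salpingectomy alone. Protocol 10.4.3 already contains a usable starting definition: "A postmenopausal state is defined as no menses for 12 months without an alternative medical cause". Add a note that a zero count on a small number at risk is uninformative. If the status is not in the database, the female-only denominator is enough, and no new data collection is being asked for.

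The cost is one sentence and one changed denominator. Sex is already collected (Protocol 8.10.1; SAP 3.5.1). The downside is a wider, less favourable interval in one supplemental row. Clinical evaluation and reporting of these events are untouched.

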6.1.1.4. Serious Adverse Events

6.1.1.4.1. Main Analysis

- Estimand: The percentage of participants reporting SAEs from vaccination through 6 months after vaccination (Section 2.2).
- Analysis set: Safety population (Section 4).
- Analysis time point: From vaccination through 6 months after vaccination.
- Analysis methodology: Descriptive statistics (Section 5.2.1).
- Intercurrent events and missing data: Missing data will not be imputed, except for partial AE start dates (Section 5.3).
- Reporting results: Counts, percentages, and the associated Clopper-Pearson 95% CIs of SAEs from vaccination through 6 months after vaccination will be provided for each vaccine group.

6.1.2. Immunogenicity Primary Endpoints

6.1.2.1. SARS-CoV-2 Omicron (XBB.1.5)-Neutralizing Titers

6.1.2.1.1. Main Analysis

- Estimands:
 - o GMTs of SARS-CoV-2 Omicron (XBB.1.5)—neutralizing titers before vaccination and at 4 weeks after vaccination.
 - O GMFRs of SARS-CoV-2 Omicron (XBB.1.5)—neutralizing titers from before vaccination to 4 weeks after vaccination.
 - o Percentages of participants with seroresponse to SARS-CoV-2 Omicron (XBB.1.5) at 4 weeks after vaccination.
- Analysis set: Evaluable immunogenicity population, all-available immunogenicity population (as applicable) (Section 4).
- Analysis time point: 4 Weeks after vaccination.
- Analysis methodology: The GMTs and the associated 2-sided 95% CIs will be provided for each vaccine group using the statistical methods described in Section 5.2.2.1. The GMFRs and the associated 2-sided 95% CIs will be provided for each vaccine group using the statistical methods described in Section 5.2.2.3. The percentages of participants with seroresponse and the associated Clopper-Pearson 95% CIs will be provided for each vaccine group (Section 5.2.1). Seroresponse is defined as achieving a ≥4-fold rise from

baseline (before the study vaccination). If the baseline measurement is below the LLOQ, the postvaccination measure of \geq 4 × LLOQ is considered seroresponse.

- Intercurrent events and missing data: Serology data deemed unevaluable because of noncompliance with the key protocol criteria will be excluded. Missing data will not be imputed.
- Reporting results: GMTs before vaccination and at 4 weeks after vaccination, GMFRs from before vaccination to 4 weeks after vaccination, and percentages of participants with seroresponse to SARS-CoV-2 Omicron (XBB.1.5) at 4 weeks after vaccination, along with the associated 2-sided 95% CIs, will be provided for each vaccine group.

Figures:

Empirical RCDCs and bar charts of GMTs and the associated 2-sided 95% CIs will be provided for SARS-CoV-2 Omicron (XBB.1.5)—neutralizing titers before and 4 weeks after vaccination for each vaccine group.

6.1.2.1.2. Supportive Analysis

Model-based and unadjusted GMRs of SARS-CoV-2 Omicron (XBB.1.5)—neutralizing titers at 4 weeks after vaccination and the associated 95% CIs will be calculated using the statistical methods described in Section 5.2.2.2 for the following comparative groups:

- BNT162b2 (Omi XBB.1.5)/RIV and placebo (Group 1) vs BNT162b2 (Omi XBB.1.5) and RIV (Group 2).
- BNT162b2 (Omi XBB.1.5)/RIV and placebo (Group 1) vs BNT162b2 (Omi XBB.1.5) and placebo (Group 3).
- BNT162b2 (Omi XBB.1.5) and RIV (Group 2) vs BNT162b2 (Omi XBB.1.5) and placebo (Group 3).

The adjusted and unadjusted difference in percentages of participants with seroresponse at 4 weeks after vaccination and the associated 2-sided 95% CIs will be calculated using the statistical methods described in Section 5.2.1 for the same comparative groups listed above.

6.1.2.2. HAI Titers

6.1.2.2.1. Main Analysis

- Estimands:
 - o GMTs of strain-specific HAI titers before vaccination and at 4 weeks after vaccination.
 - o GMFRs of strain-specific HAI titers from before vaccination to 4 weeks after vaccination.

- Percentages of participants achieving strain-specific HAI seroconversion at 4 weeks after vaccination.
- o Percentages of participants with strain-specific HAI titers ≥1:40 before vaccination and at 4 weeks after vaccination.
- Analysis set: Evaluable immunogenicity population, all-available immunogenicity population (as applicable) (Section 4).
- Analysis time point: 4 Weeks after vaccination.
- Analysis methodology: The GMTs and the associated 2-sided 95% CIs will be provided for each vaccine group using the statistical methods described in Section 5.2.2.1. The GMFRs and the associated 2-sided 95% CIs will be provided for each vaccine group using the statistical methods described in Section 5.2.2.3. The percentages of participants achieving HAI seroconversion and with HAI titers ≥1:40 and the associated Clopper-Pearson 95% CIs will be provided for each vaccine group (Section 5.2.1). Seroconversion is defined as an HAI titer <1:10 prior to vaccination and ≥1:40 at the time point of interest, or an HAI titer of ≥1:10 prior to vaccination with a minimum 4-fold rise at the time point of interest.
- Intercurrent events and missing data: Serology data deemed unevaluable because of noncompliance with the key protocol criteria will be excluded. Missing data will not be imputed.
- Reporting results: For each influenza virus strain, GMTs before vaccination and at 4 weeks after vaccination, GMFRs from before vaccination to 4 weeks after vaccination, percentages of participants achieving HAI seroconversion at 4 weeks after vaccination, and percentages of participants with HAI titers ≥1:40 before vaccination and at 4 weeks after vaccination, along with the associated 2-sided 95% CIs, will be provided for each vaccine group.

Figures:

Empirical RCDCs and bar charts of GMTs and the associated 2-sided 95% CIs will be provided for each strain-specific HAI titer before and 4 weeks after vaccination for each vaccine group.

6.1.2.2.2. Supportive Analysis

The model-based and unadjusted GMRs of strain-specific HAI titers at 4 weeks after vaccination and the associated 95% CIs will be calculated using the statistical methods described in Section 5.2.2.2 for the following comparative groups:

• BNT162b2 (Omi XBB.1.5)/RIV and placebo (Group 1) vs BNT162b2 (Omi XBB.1.5) and RIV (Group 2).

- BNT162b2 (Omi XBB.1.5)/RIV and placebo (Group 1) vs RIV and placebo (Group 4).
- BNT162b2 (Omi XBB.1.5) and RIV (Group 2) vs RIV and placebo (Group 4).

The adjusted and unadjusted difference in percentages of participants with HAI seroconversion at 4 weeks after vaccination and the associated 2-sided 95% CIs will be calculated using the statistical methods described in Section 5.2.1 for the same comparative groups listed above.

6.2. Secondary Endpoint(s)

Not applicable.

6.3. Other Safety Summaries and Analyses Endpoint(s)

Not applicable.

6.4. Exploratory Endpoints

6.4.1. SARS-CoV-2 Omicron (XBB.1.5)-Neutralizing Titers and HAI Titers

- Estimands:
 - GMTs of SARS-CoV-2 Omicron (XBB.1.5)—neutralizing titers and strain-specific HAI titers before vaccination and at 6 months after vaccination.
 - O GMFRs of SARS-CoV-2 Omicron (XBB.1.5)—neutralizing titers and strain-specific HAI titers from before vaccination to 6 months after vaccination.
 - o Percentages of participants with seroresponse to SARS-CoV-2 Omicron (XBB.1.5) and achieving strain-specific HAI seroconversion at 6 months after vaccination.
 - o Percentages of participants with strain-specific HAI titers ≥1:40 before vaccination and at 6 months after vaccination.
- Analysis set, analysis methodology, and intercurrent events and missing data are the same as described above for the immunogenicity primary endpoints (Section 6.1.2).
- Reporting results: GMTs before vaccination and at 6 months after vaccination, GMFRs from before vaccination to 6 months after vaccination, percentages of participants with seroresponse to SARS-CoV-2 Omicron (XBB.1.5) at 6 months after vaccination, percentages of participants achieving HAI seroconversion at 6 months after vaccination, and percentages of participants with HAI titers ≥1:40 before vaccination and at 6 months after vaccination, along with the associated 2-sided 95% CIs, will be provided for each vaccine group. This analysis may be conducted in a selected subset of participants.

